Design and Overview (Table 3): This is a randomized, double-blind, placebo-controlled trial examining the effects of suvorexant (Merck & Co., Kenilworth, NJ), a dual orexin receptor antagonist that is FDA approved for insomnia, on sleep and PTSD symptom reduction following WNE. We will employ our successful recruitment strategies, including flyers, outreach activities, and referral from previous participants. Potential participants will initially be screened over the phone or in person, and those who meet initial criteria will be invited to the Clinical Research Unit (CRU) at Howard University to complete a consent procedure, questionnaires, a clinical interview, a physical examination, and urine tests. Participants who meet the selection criteria will be invited to complete two pairs of 30-minute WNE sessions and four overnight PSG recordings [screening, baseline, between WNE sessions (twice)]. Both pairs of WNE sessions will occur at 8PM and 8AM in the following morning with intervening sleep. The second pair will occur one week after the first pair. Four WNE sessions are

Table 3. Study Design

Day	1	2	3	4	5	11	12	18
Consent; Questionnaires	X							
Physical exam	X							
Vital signs	X				X		X	
Urine tests	X							
CAPS (lifetime & past month)	X							
SCID	X							
CAPS (past week)				X	X		X	
C-SSRS	X			X	X		X	
Alertness scale				X	X		X	
Adverse event assessment	X			X	X	X	X	
WNE (AM)					X		X	
WNE (PM)					X		X	
Suvorexant or placebo					X		X	
PSG		X screen	X baseline		X		X	

needed because the majority of participants in the preliminary study did not achieve remission until after completing the second pair of WNE. Participants will be stratified by gender and randomly assigned to either suvorexant or placebo. After the 1st evening WNE, a 10 mg tablet of suvorexant or placebo will be administered orally 30 minutes before bedtime. If the medication is well tolerated, the dose will be increased to 20 mg at the 2nd administration after the 3rd WNE. The recommended dose is 10mg, and the maximum recommended dose is 20mg.⁶⁰ The 1-week CAPS will be administered before the 1st and 3rd sessions and at 1-week follow-up.

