Pulse rate. The pulses will be continuously recorded during the 5-min baseline and the 30-min WNE through a finger pulse transducer of the PowerLab system (ADIInstruments, Colorado Springs, CO). Data will be visually inspected using the LabChart software (ADIInstruments), and segments with artifacts will be excluded. The average pulse rates for the 5-min baseline and each 2-minute epoch during WNE will be computed. A baseline-corrected highest average pulse rate for each session will be computed by subtracting the session's average baseline pulse rate from the highest average pulse rate in the session. The baseline correction will be performed to correct for circadian influences on pulse rates.⁶⁵⁻⁶⁷

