Study Medication Administration: Participants will be stratified for gender and randomly assigned to either suvorexant or placebo before the 1st WNE. Suvorexant or placebo will be administered orally after the 1st and 3rd WNE, 30 minutes before the participant's habitual bedtime. If the participant well tolerates 10mg, the dose will be increased to 20mg at the 2nd administration. Participants will have continuous access to research nurses during the sleep recording. In the following morning, a nurse will assess possible adverse effects.

Written Narrative Exposure (WNE): We will use a procedure similar to the one used in the R21 study. Sessions will begin at 8PM and approximately 8AM. The morning sessions will not start until the participant's alertness level reaches the level he/she indicated in the morning after the baseline PSG recording. The participant will sit at a desk in a private room with a facilitator, and a pulse transducer will be attached to the distal of the middle finger of his/her non-dominant hand placed on the desk. After a 10-minute acclimatization period, a 5-minute baseline pulse recording will begin. At the end of the baseline, the facilitator will provide instructions to write in as much detail as possible about his/her index trauma including what

happened, how s/he felt, and what s/he perceived and thought and to use the entire 30 minutes. The facilitator will also instruct the participant to orally report an overall level of distress on a scale from 0 – 100 [subjective units of distress scale (SUDS)] at baseline, every 10 minutes, and at the end of the writing period. The facilitator will remain in the same room during the writing to obtain SUDS scores and to assist and encourage the participant if necessary. At the end of the writing period, if warranted, the facilitator will instruct the participant in relaxation techniques for ≤10 minutes. Participants will not be dismissed until distress is minimal.

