Statistical Analysis Plan

Official Title: Can Blocking the Orexin System Enhance Sleep's Benefits to Therapeutic Exposure for PTSD?

NCT number: NCT02849548

Date of the Document: July 7,2016

Data Analysis Plan: Initially, data will be pre-screened for errors, outliers, normality of distributions, and any necessary modifications such as transformation will then be conducted. The suvorexant and placebo groups will be compared on demographics and baseline measures using *t*-tests or chi-squared tests to examine group comparability. Fig. 1 describes each hypothesis. **Hypothesis 1a:** The primary comparison will be between the 2 groups (suvorexant vs. placebo) and sleep parameters measured at 3 time points (baseline, post-Session 1, and post-Session 3). A repeated-measures ANOVA will be performed to examine whether there is a Group x Time interaction effect on each sleep parameter of interest (i.e., N3, WASO, and REM sleep). If a significant interaction effect is found, group comparisons will be performed at each time point. **Hypothesis 1b:** A repeated-measures ANOVA will be performed to examine whether there is a Group x Time interaction effect on CAPS scores. In addition, 2(Group) x 2(Time) ANOVAs will be performed to examine if there is an interaction effect on intersession habituation between Session 1 & 2 and between Session 3 & 4, using a baseline-corrected highest average pulse rate as a dependent variable. **Hypothesis 1c:** To examine indirect effects of suvorexant on PTSD through the mediator, post-WNE sleep change, a path analysis using bootstrapping procedures will be performed for each sleep parameter of interest using SPSS macros developed by Preacher & Hayes.⁷⁰ Baseline CAPS scores will be included as a covariate. The same method will be used to examine indirect effects of suvorexant on intersession habituation.

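### The Session 3 v Session 4 pulse test measures only the second-night increment, and no planned pulse analysis measures one-week retention or the cumulative effect of both treated nights

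*SAP*

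**What the plan says.** The SAP (Data Analysis Plan, Hypothesis 1b) specifies a repeated-measures ANOVA for CAPS. For pulse it specifies separate 2 x 2 ANOVAs that test for "an interaction effect on intersession habituation between Session 1 & 2 and between Session 3 & 4". The outcome for both of these tests is stated in the same sentence of the SAP: "using a baseline-corrected highest average pulse rate as a dependent variable".

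The Protocol fixes the order of events:

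- Study Medication Administration: participants are "randomly assigned to either suvorexant or placebo before the 1st WNE", and "Suvorexant or placebo will be administered orally after the 1st and 3rd WNE".
- Design and Overview: "Both pairs of WNE sessions will occur at 8PM and 8AM in the following morning with intervening sleep". The second pair follows the first by one week.
- Pulse rate: the baseline correction is made by "subtracting the session's average baseline pulse rate from the highest average pulse rate in the session". It removes that session's resting level and does not refer back to a pre-drug session.
- Design and Overview, on CAPS: "The 1-week CAPS will be administered before the 1st and 3rd sessions and at 1-week follow-up". The CAPS analysis therefore spans the whole course.

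Neither document specifies a pulse analysis that compares Session 3 or Session 4 with Session 1, or one that uses all four sessions together.

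**The concern.** Session 1 is the only exposure session before any drug. Session 3 comes after the first dose and the first treated night. It is the pre-dose value for the second night, but it is not a pre-treatment value for the trial. If suvorexant lowers pulse reactivity and some of that lasts a week, the arms already differ at Session 3. A change measured from Session 3 removes that difference.

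The Protocol justifies four sessions on the ground that most participants in the preliminary study reached remission only after the second pair. The state after both pairs is thus a main reason for the design. For CAPS the plan measures it; for pulse it does not. Intersession habituation is named in Aim 1 and is used again as an outcome in Hypothesis 1c. At stake are an untested cumulative effect and a second-pair result that could be misread, because the SAP does not say which effect it estimates.

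**Working it through.** **Plan's own figure.** The only sample size given for Hypothesis 1b is 12 participants at f = 0.40, taken from a prazosin trial. For a Group x Time interaction with 2 groups and m = 3 times, and assuming correlation 0.5, sphericity and 80% power:

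- noncentrality = f² x N x m / (1 - correlation) = 0.16 x 12 x 3 / 0.5 = 11.52, on 2 and 20 df;
- power = 0.81, so N = 12 reproduces.

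Three times matches the CAPS schedule. No figure is given for the two-session pulse tests.

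**What the Session 3 v 4 interaction estimates.** Count lower pulse on suvorexant as benefit. Let d1 be the first-night benefit, r the fraction of it present at Session 3, and d2 the second-night gain.

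- Group difference at Session 2: d1
- Group difference at Session 3: r x d1
- Group difference at Session 4: r x d1 + d2
- Session 1 v 2 interaction: d1 - 0 = d1
- Session 3 v 4 interaction: (r x d1 + d2) - r x d1 = d2

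The retained part drops out whatever the effect size or correlation, provided it is equal at Sessions 3 and 4.

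**Illustration.** Inputs: 27 per arm (SAP, Power considerations), two-sided 0.05, session SD 1. Effects are in SD units, with the same correlation, 0.5, between all sessions. The effects and the correlation are assumptions. A 2 x 2 interaction is a t-test on change.

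- SE for change = sqrt[2(1 - 0.5) x 2/27] = 0.272; at 0.8 SD, 0.8/0.272 = 2.94, power 82%.
- SE adjusted for Session 1 = sqrt[(1 - 0.5²) x 2/27] = 0.236; at 0.8 SD, 0.8/0.236 = 3.39, power about 91%.

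With d1 = 0.8 throughout:

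| r | d2 | Difference at S3 | Difference at S4 | S3 v S4 estimate | S3 v S4 power | S4 adjusted for S1, power |
|---|---|---|---|---|---|---|
| 0 | 0.8 | 0 | 0.8 | 0.8 | 82% | 91% |
| 0.5 | 0.4 | 0.4 | 0.8 | 0.4 | 30% | 91% |
| 1 | 0 | 0.8 | 0.8 | 0 | 5% (the null rate) | 91% |
| 0.5 | 0.8 | 0.4 | 1.2 | 0.8 | 82% | >99% |
| 1 | 0.8 | 0.8 | 1.6 | 0.8 | 82% | >99% |

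Simulation of the third row (20,000 trials) gave a mean Session 3 v 4 interaction of 0.001 with 5.2% rejections; Session 1 v 2 rejected in 82%.

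The last two rows separate the two influences. With d2 held at 0.8, Session 3 v 4 power is 82% whether none, half or all of the first-night benefit is retained. Power falls only when d2 is smaller.

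**Sensitivity to correlation.** For a 0.8 SD difference at Session 4, adjustment for Session 1 gives about 85%, 91% and 98% power at correlations 0.3, 0.5 and 0.7. An unadjusted Session 1 to 4 change gives 68%, 82% and 96%.

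**Unequal correlations.** Sessions 12 hours apart may correlate more strongly than sessions a week apart. Take 0.7 within a pair and 0.3 across the week (assumed):

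- nothing retained, d2 = 0.8: planned test 96%, Session 1-adjusted test about 85%;
- half retained, d2 = 0.4: planned test 46%, Session 1-adjusted test about 85%.

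**The case against.** The strongest reply is that this is a choice of estimand. The plan asks about change within each pair, across one night of sleep on drug or placebo. Session 3 is the proper pre-dose reference for the second night, and the contrast answers the question as written. That stands. It is also why the Session 3 v 4 contrast should not be displaced: the two contrasts estimate different things, and under unequal correlations the planned one can be the more powerful.

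A reader might infer several stronger things that the documents do not support.

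- *Retention destroys the power of the second test.* It does not. Full retention with a fixed Session 4 difference means that the second night added nothing, and an estimate of zero is then correct. The Protocol plans a higher second dose where the first is tolerated, so zero gain is not evidently what it expects.
- *The CAPS and pulse parts of Hypothesis 1b contradict each other.* The CAPS before Session 3 shows that carry-over of symptoms is measured. It does not show that lower Session 3 pulse is predicted. The figure that sets out the hypotheses is not available to this review.
- *A null second pair will be read as no habituation.* No section sets such a rule, and the Session 1 v 2 test would stand beside it.
- *A floor in pulse will reverse the interaction.* This is possible, but no figure in the documents bears on it.

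Pulse is also an additional analysis; the SAP attaches the primary comparison to sleep under Hypothesis 1a. What remains is the gap in coverage and the missing label.

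**Conclusion.** The point holds as a gap in the pulse analysis; neither planned test is invalid. Session 1 v 2 is sound for the first night, and Session 3 v 4 is sound for the second-night increment. No planned pulse test measures retention at one week or the cumulative effect, although the cumulative result is part of the Protocol's reason for a second pair.

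The cancellation is algebraic and needs only that the retained benefit be equal at Sessions 3 and 4. If it fades overnight or meets a floor, cancellation is inexact. The size depends on assumption: with 27 per arm and common correlation 0.5, a 0.8 SD cumulative difference has about 91% power when adjusted for Session 1, while the planned second test sees anything from 0 to 0.8 SD of it. The documents give no effect size, SD or correlation for pulse.

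**What to change.** In the SAP, Hypothesis 1b:

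1. Keep the Session 3 v 4 interaction and label it the second-night increment. State that a null there is not evidence against habituation if the arms already differ at Session 3.
2. Add prespecified group comparisons of baseline-corrected peak pulse at Session 3 (retention) and Session 4 (cumulative), adjusted for the Session 1 value and the gender stratifier. One mixed model of Sessions 2 to 4, with Session 1 as covariate and a group effect at each session, would do this.
3. For the first pair, analyse Session 2 adjusted for Session 1 in place of the change. This is a separate gain in efficiency: about 91% against 82% power for 0.8 SD at correlation 0.5.
4. State which habituation measure enters Hypothesis 1c; if it is the Session 3 to 4 change, give it the same label.

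The cost is a few lines of text and one or two more contrasts to interpret. All the data are already to be collected.

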Clinical interviews. Structured interviews will be conducted by clinically trained staff and will be reviewed weekly in a consensus conference with the candidate (a licensed psychologist) and the primary mentor (a board certified psychiatrist). The CAPS⁵⁵ will be administered to assess current (past month and past week) and lifetime PTSD diagnosis and severity associated with the index trauma. The Structured Clinical Interview for DSM-5 (SCID)⁶² will be administered to assess current and lifetime psychiatric diagnoses and confirm inclusion criteria. The C-SSRS⁶³ will be administered at the initial visit to assess suicidal ideation and behaviors in lifetime and past 6 months and at subsequent visits to assess any changes since the previous visit. The PI will be immediately notified if a participant indicates concerning suicidal ideation or behaviors.

Sleep recordings. PSG recordings in the CRU will use a Natus/Embla (Pleasanton, CA) Titanium PSG unit including two central, frontal, and occipital EEG leads, two electrooculograms, chin and limb electromyograms, and an electrocardiogram. Participants will be instructed to go to bed at their habitual bedtime and wake up at 8 AM. Screening for sleep disordered breathing will be performed using the screening night data. Visual scoring of sleep records will be done following the American Academy of Sleep Medicine Manual, Version 2.3.⁶⁴ We will calculate standard PSG sleep parameters including total sleep time, WASO, the percentage and the duration of each sleep stage, and REM density using the REMLogic software (Natus/ Embla). Sleep changes from baseline to post-WNE will be computed by subtracting baseline measures from respective measures obtained during sleep following the 1st and 3rd WNE sessions.

Alertness visual analogue scale (VAS). Participants will complete an alertness VAS upon awakening in the morning after PSG recordings. The VAS is a 100 mm horizontal line with a label "very sleepy" on the left end and "very alert" on the right end. Participants will be place a

slash mark on the scale to indicate their alertness at the moment. A morning WNE session will not begin until the participant's alertness level reaches the level he/she indicated in the morning after the baseline PSG recording.

Adverse event assessment. Participants will be queried regarding the presence of any symptoms or concerns before and after the medication administration.

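### The habituation mediation model in Hypothesis 1c names only baseline CAPS as a covariate and omits the evening session's peak pulse, leaving the sleep-to-habituation path open to confounding by evening arousal

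*SAP*

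**What the plan says.** The SAP's Data Analysis Plan describes Hypothesis 1c as a mediation analysis. The drug is the exposure, and for "the mediator, post-WNE sleep change, a path analysis using bootstrapping procedures will be performed for each sleep parameter of interest". On adjustment it says only: "Baseline CAPS scores will be included as a covariate". It then extends the analysis to the second outcome: "The same method will be used to examine indirect effects of suvorexant on intersession habituation". No other covariate is named.

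Habituation is introduced under Hypothesis 1b, where the SAP tests for this: "interaction effect on intersession habituation between Session 1 & 2 and between Session 3 & 4". The measure to be analysed is named in the same sentence: "using a baseline-corrected highest average pulse rate as a dependent variable". Sessions 1 and 3 are evening sessions; Sessions 2 and 4 are the following mornings. The SAP does not say whether the path model's outcome is the evening-minus-morning difference or the morning value.

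The Protocol's sleep recordings section builds the mediator by subtracting the baseline night from "measures obtained during sleep following the 1st and 3rd WNE sessions". The mediator night therefore lies between the two sessions being compared.

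Evening arousal is already recorded. Under Pulse rate: "A baseline-corrected highest average pulse rate for each session will be computed". Under Written Narrative Exposure: "The facilitator will also instruct the participant to orally report an overall level of distress", on a 0-100 scale at baseline and during writing. Study drug is given after Sessions 1 and 3.

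**The concern.** Randomisation protects the drug-to-sleep path and the total effect of drug on habituation. It does not protect the sleep-to-habituation path, because nobody is randomised to a night's sleep. That path needs adjustment for anything that affects both the night's sleep and the habituation score.

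The evening peak pulse is the obvious candidate. It affects the outcome by construction: a participant with a high evening peak has more room to fall by morning. It also comes just before the sleep mediator, and a participant more aroused by the evening session may sleep worse that night.

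The two adjustments already in the plan do not deal with this. The within-session pulse correction is there for circadian level, not evening reactivity. Baseline CAPS is a symptom interview and would stand in for that evening's arousal only as far as the two correlate.

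At stake is the question in the trial's title, whether the drug works through sleep. The SAP says the results will inform later grant applications. A diluted, wrong-signed or inflated sleep path would mislead them.

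**Working it through.** The plan gives no sample size, power or effect size for this model (it calls the indirect effects unknown), so there is no planned figure to reproduce.

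**Inputs from the documents.** 54 completers, 27 per group; alpha 0.05; an effect of the drug on WASO of f = 0.37 in absolute value (SAP, Power considerations). With two equal groups d = 2f = 2 × 0.37 = 0.74 SD. That f is for one night at 20/15 mg, while the Protocol's first administration is 10 mg, so a weaker effect of 0.5 SD is also shown.

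**Assumptions, not in the documents.** Evening-morning pulse correlation r = 0.5; link from evening arousal to that night's WASO change c = 0.2 to 0.3; correlation of CAPS with evening arousal q = 0.3; evening peak measured without error. WASO stands for the mediator; N3 and REM were not modelled.

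**Model (SD units).** E is the evening peak, T the drug, M the WASO change and Y the morning peak:
- M = −aT + cE + noise
- Y = rE + bM + noise
- difference score H = E − Y = (1 − r)E − bM − noise

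The hypothesis corresponds to b > 0: more wake after sleep onset, higher morning peak, less habituation.

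**Bias with CAPS only.** Omitting E shifts the coefficient of M by

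k·c·(1 − q²) / [c²(1 − q²) + 1 − c²],

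with k = 1 − r for the difference score and k = r for the morning value. Here 1 − q² = 0.91.
- c = 0.2: 0.5 × 0.2 × 0.91 = 0.091; divisor 0.04 × 0.91 + 0.96 = 0.996; bias 0.09.
- c = 0.3: 0.5 × 0.3 × 0.91 = 0.1365; divisor 0.09 × 0.91 + 0.91 = 0.992; bias 0.14.

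**Direction.** The shift is positive for both outcomes, but the outcomes point opposite ways.
- *Difference score:* the true coefficient is −b. With b = 0.3, the expected estimate moves from −0.30 to between −0.21 and −0.16, so the bias runs against the hypothesis.
- *Morning value:* the true coefficient is +b. With b = 0.3, the expected estimate moves from 0.30 to between 0.39 and 0.44, so the bias favours the hypothesis.

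**Sensitivity.** At c = 0.3, q = 0.3, the difference-score bias is 0.19 at r = 0.3 and 0.08 at r = 0.7; for the morning value these two figures swap. CAPS removes little: at c = 0.3, r = 0.5 the bias is 0.15, 0.14 and 0.12 for q = 0, 0.3 and 0.5. The bias is zero if c = 0, and also zero for a difference score if r = 1.

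**The planned test.** Simulated percentile-bootstrap test of the indirect effect, difference score, N = 54, c = 0.2 to 0.3:

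| Drug effect on sleep | Quantity | CAPS only | CAPS + evening peak |
|---|---|---|---|
| 0.74 SD | False positives (b = 0) | 8-12% | 2-5% |
| 0.5 SD | False positives (b = 0) | 5-7% | 2-5% |
| 0.74 SD | Power (b = 0.3) | 16-24% | 46-51% |
| 0.5 SD | Power (b = 0.3) | 9-14% | 26-27% |

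The 2-5% covers both drug effects. A separate run at 0.74 SD (800 trials, 400 bootstrap draws) gave 7.5% and 13.8% with CAPS only, and 3.5-6.0% with the evening peak over a wider set of scenarios. Simulation error is about one percentage point: √(0.1 × 0.9 / 800) = 0.011.

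**If arousal does not affect sleep.** At c = 0 the residual variance of the difference score is (1 − r)²(1 − q²) + (1 − r²) = 0.25 × 0.91 + 0.75 = 0.98 with CAPS only, and 0.75 with the evening peak. The reduction is 0.23 / 0.98, just under a quarter.

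**Effect on the open outcome definition.** Because H = E − Y, once E is in the equation the two outcomes give the same sleep coefficient apart from sign.

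**The case against.** The strongest objection is that nothing in the documents shows that evening arousal affects that night's sleep. The mediator is a change from a baseline night, so stable differences between sleepers are already subtracted. This stands: every figure above rests on an assumed link, and a reader might infer that the path is biased as a matter of fact. The documents support only that it is open to confounding.

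A reader might also infer that the bias necessarily works against the hypothesis and hides a real benefit. That requires the outcome to be a difference score, which the SAP does not specify; with the morning value it works the other way. Even with a difference score, a bias of 0.09 to 0.14 takes roughly a third to a half off a true path of 0.3. It does not cancel it.

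Testing the sleep-to-habituation coefficient alone gives more striking figures: false positives of 10-17% with CAPS only, and power of about 64% once evening pulse is added. The plan tests the indirect effect, so those figures do not describe it. At the assumed effect sizes the planned test remains underpowered after adjustment.

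The carried-over method could be read as adjusting each outcome for its own baseline, since CAPS is the PTSD outcome's baseline. For habituation that would be the evening pulse. The reading is possible, and the figure said to describe the hypotheses is not in the public text. But the SAP names only CAPS; if the other reading is meant, one sentence settles it.

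Finally, Hypothesis 1a is labelled the primary comparison, and mediator-outcome confounding is a general limit of mediation analysis. Both are true and limit the weight of the point. They do not explain leaving out a value that is already collected.

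**Conclusion.** The point holds as an omission that leaves one path of the model unprotected. The only named covariate for the habituation mediation is a symptom score, and the evening peak pulse is left out although it precedes the mediator and forms part of the habituation contrast.

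Under the stated assumptions the cost is moderate. False positives for the planned test rise above nominal mainly at the larger drug effect on sleep, and power is about half or less of what the adjusted model gives. The size depends on an arousal-sleep link that the documents do not quantify, and the sign depends on an outcome they do not define. Adjustment is worthwhile even without the link, because residual variance still falls.

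The randomised comparison of habituation under Hypothesis 1b is not affected.

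**What to change.** In the SAP under Hypothesis 1c:

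1. State the habituation outcome for the path model (evening-minus-morning difference or morning value) for each session pair.
2. Add the same evening session's baseline-corrected peak pulse as a covariate alongside baseline CAPS.
3. Session 1-2 pair: the Session 1 value is pre-dose, so enter it in both the sleep and the outcome equations.
4. Session 3-4 pair: the Session 3 value follows the first dose and may itself be affected by treatment, so simple adjustment may not be enough. Report the adjusted model with that caveat and treat it as a sensitivity analysis.
5. Repeat the models with evening SUDS as a sensitivity analysis. Its effect was not simulated here.

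The cost is SAP wording and one degree of freedom in the main model. No new data are needed.
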